9.2 MEASUREMENT OF TREATMENT COMPLIANCE

Not applicable in this study.

10.0 EFFICACY ANALYSES

The efficacy analyses will be based on the ITT Population. *Baseline* for efficacy is defined as the last nonmissing assessment before the first dose of study treatment. All statistical tests will be 2-sided hypothesis tests performed at the 5% level of significance for main effects. All confidence intervals will be 2-sided 95% confidence intervals, unless stated otherwise. There will be no adjustments for multiple comparisons.

Mis-stratified participants, if any, will be analyzed based on the stratification group to which the participants were assigned to (i.e. the planned stratification group used at the time of randomization).

Unless otherwise stated, missing values will be imputed (see details below) only for the primary efficacy variable.

10.1 PRIMARY EFFICACY VARIABLE

The primary efficacy variable is the change from baseline in the average number of urinary incontinence episodes (UIEs) per day. The primary timepoint is week 12.

The number of UIEs per day will be recorded in the participant bladder diary over 3 consecutive days at any time during the screening period for the screening diary, and over 3 consecutive days during the week prior to each post baseline visit. The average number of UIEs per day will be calculated as the total number of episodes recorded in the 3-day bladder diary divided by the total number of valid diary days (see [Section 15.2](#)). Calculation of averages will employ available “valid diary days” data without imputation. If no “valid diary days” data are available for the consecutive 3-day period, that average will be considered missing for that participant. The last-observation-carried-forward (LOCF) approach will be used to impute missing postbaseline average values.

For the primary efficacy analysis, the null hypothesis is that there is no difference between each (BOTOX and Hydrogel admixture group) and (placebo and Hydrogel admixture) in the mean change from baseline in daily average number of UIEs at week 12. The alternative hypothesis is that there is a difference between each (BOTOX and Hydrogel admixture group) and (placebo and Hydrogel admixture group) in the mean change from baseline in daily average number of UIEs at week 12.

The hypotheses will be tested using an ANCOVA model with baseline value as covariate and treatment group and sex (male, female) as factors. Pairwise comparisons will be performed for each BOTOX group versus placebo using t-tests of the least square means from the ANCOVA model. The stratification factor of baseline UUIEs (≤ 9 or > 9 episodes/day) is not included in the model due to a very high correlation between UIEs and UUIEs (Pearson’s correlation coefficient = 0.97 based on phase 2 data (191622-077 study)).

A sensitivity analysis of the primary efficacy variable will be performed using the same ANCOVA model discussed above. This will be based on observed data only (i.e. no LOCF imputation of missing postbaseline average values).

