treatment groups, including 4 BOTOX arms and 1 placebo arm. Participants who receive study treatment in Stage 1 are not eligible to enroll in Stage 2.

- At Day 1, participants in both Stage 1 and Stage 2 will be randomized centrally to receive either a single treatment of BOTOX or matching placebo via intravesical instillation. Randomization will be stratified by baseline urgency urinary incontinence episodes and sex for Stage 2 only.
- In Stage 1, participants will be randomized in a 4:1 ratio to receive either BOTOX (100 U, 300 U, 400 U [optional], 500 U) or placebo. For each cohort in Stage 1, an unblinded safety review by the DRC will be performed when all participants reach Week 6. Enrollment into the next cohort at the higher dose will begin only after the DRC has deemed it safe to proceed to the next cohort.
- In Stage 2, participants will be randomized in a 1:1:1:1:1 ratio for treatment with either BOTOX 100 U, BOTOX 300 U, BOTOX 400 U, BOTOX 500 U (or 200 U), or placebo.
- Confirmation of the BOTOX doses for investigation in Stage 2 will occur after review of unblinded safety data from the 500 U Cohort in Stage 1 by the DRC. Based on this review, the DRC will have the option to replace the BOTOX 500 U treatment group with BOTOX 200 U in Stage 2.

• Visit Schedule:

BOTOX® (Botulinum Toxin Type A)  
Purified Neurotoxin Complex

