CFB ANCOVA	
 
• Continuous descriptives and standard error (SE) for baseline, postbaseline, with LOCF, and CFB values
 
• Estimates derived from mixed model for CFB value controlling for factors (treatment group and stratification variables) and covariates (baseline value) 
 
○ Least squares (LS) means and standard errors
 
○ LS mean differences, standard errors, and 95% confidence intervals vs placebo
 
○ P-values from contrast t-test comparing [BOTOX dose groups vs placebo]
 
 
 
• N1 = participants with nonmissing values at baseline
 

CFB ANCOVA Sensitivity	
 
• Continuous descriptives and standard error (SE) for baseline, postbaseline with only observed values, and CFB values
 
• Estimates derived from mixed model for CFB value controlling for factors (treatment group and stratification variables) and covariates (baseline value) 
 
○ Least squares (LS) means and standard errors
 
○ LS mean differences, standard errors, and 95% confidence intervals vs placebo
 
○ P-values from contrast t-test comparing [BOTOX dose groups vs placebo]
 
 
 
• N1 = participants with nonmissing values at both baseline and the specified postbaseline analysis visit
 

**BOTOX® (Botulinum Toxin Type A)  
Purified Neurotoxin Complex**

Methodology	Description
Responder	
 
• Categorical descriptives for responders and nonresponders           
 
◦ Nonresponders include:               
 
▪ Participants who do not meet responder criteria
 
▪ Participants with no postbaseline values
 
 
 
 
 
• 95% confidence interval for the proportion
 
• Estimates derived from Cochran-Mantel-Haenszel (CMH) model controlling for stratification factors           
 
◦ Mantel-Haenszel (MH) odds ratios (ORs) and confidence intervals vs placebo
 
◦ P-values for the adjusted odds ratio of BOTOX dose groups vs placebo
 
 
 
• N1 = all participants unless otherwise specified
 

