15.9 CHARACTER VALUES OF CLINICAL LABORATORY PARAMETERS

If the reported value of a clinical laboratory parameter cannot be used in a statistical summary table because, for example, a character string is reported for a parameter of the numeric type, a coded value must be appropriately determined for use in the statistical analyses. The actual values, however, as reported in the database will be presented in the data listings.

shows examples of how some possible laboratory results should be coded for the analysis
[Table 15.9-1](#).

[figure not shown]
Table 15.9-1 Examples of Coding Special Character Values for Clinical Laboratory Parameters

Laboratory Test, SI Unit	Possible Laboratory Results	Coded Value for Analysis
CHEMISTRY		
ALT, U/L	< 5	5
AST, U/L	< 5	5
Bilirubin, total, μ mol/L	< 2	2
URINALYSIS		
Glucose, mmol/L	= OR $> 55, \geq 55, > 0$	Positive
	≤ 0 , negative	Negative
pH	$> 8.0, \geq 8.0$	8.0
	≥ 8.5	8.5
Protein	= OR $> 3.0, \geq 3.0, > 0$	Positive
	≤ 0	Negative

ALT = alanine aminotransferase; AST = aspartate aminotransferase; SI = *Le Système International d'Unités* (International System of Units).

[figure not shown]
16.0**CHANGES TO ANALYSES SPECIFIED IN PROTOCOL**

It is stated in [protocol](#) that all ANCOVA models will include both stratification factors (sex and baseline UUIEs per day) as independent variables. However, some of the ANCOVA models include only sex (male, female) due to the high correlation (observed in previous Allergan studies) between baseline UUIEs (≤ 9 or > 9 episodes/day) and some of the dependent variables derived from the bladder diary data.

ALLERGAN

1839-201-021 Statistical Analysis Plan for Stage 2

Date (DD/MMM/YYYY)/Time (PT)	Signed by:	Justification
10-Jan-2020 15:12 GMT-080		Biostatistics Approval
11-Jan-2020 07:23 GMT-080		Biostatistics Approval
13-Jan-2020 12:58 GMT-080		Biostatistics Approval
15-Jan-2020 08:23 GMT-080		Clinical Development Approval

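### The Stage 2 primary ANCOVA omits the randomised UUIE stratum that the protocol model includes, and neither reason in the SAP justifies this; the effect on the test is small

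*SAP*

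**What the plan says.** **Allocation.** The protocol synopsis states: "Randomization will be stratified by baseline urgency urinary incontinence episodes and sex for Stage 2 only". Protocol 5.4 and 7.3 give the cut-off (≤ 9 or > 9 per day), and 5.4 gives balance across arms as the purpose.

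**Protocol model.** Protocol Table 10-3, under CFB ANCOVA, reads: "Estimates derived from mixed model for CFB value controlling for factors (treatment group and stratification variables) and covariates (baseline value". The endpoint table in 10.3.2.2 assigns this method to the primary endpoint.

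**SAP model.** Stage 2 SAP 10.1 reads: "The hypotheses will be tested using an ANCOVA model with baseline value as covariate and treatment group and sex (male, female) as factors". It then says that the UUIE stratum "is not included in the model due to a very high correlation between UIEs and UUIEs" and supports this with a Pearson "correlation coefficient = 0.97 based on phase 2 data (191622-077 study". The observed-data sensitivity analysis in 10.1 uses the same reduced model.

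**Declared change.** Stage 2 SAP 16.0 lists the departure from the protocol. The reason given there is high correlation between the two-level UUIE factor and "some of the dependent variables derived from the bladder diary data".

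**Related text.** In SAP 10.2 the micturition model also omits the stratum. The volume-voided model keeps a ≤ 9 / > 9 factor, but labels it UIEs where randomisation used UUIEs. SAP 10.0 already settles which stratum value to use: "Mis-stratified participants, if any, will be analyzed based on the stratification group to which the participants were assigned to".

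**The concern.** An analysis normally adjusts for the factors used to allocate treatment. Stratifying makes the arms more alike on the stratum, and a model that ignores the stratum does not credit that balance, so its standard errors can be larger than they need be. Here the protocol followed the convention and the SAP departs from it for the trial's primary test.

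Neither reason given supports the departure. Section 10.1 cites a correlation between two counts, whereas the term left out is a two-level factor. Section 16.0 cites correlation with outcomes, which is what makes a covariate worth including. At stake is some precision in all four dose-placebo comparisons, in a trial planned at about 72% power, and a primary model whose stated rationale would not stand up if questioned.

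**Working it through.** **1. The plan's own figure.** Inputs from Stage 2 SAP 13.0: 50 per group, difference 1.8, SD 3.5, two-sided alpha 0.05. The standard error is 3.5 × √(2/50) = 0.700, and 1.8 / 0.700 = 2.571. Power is 72.1% (noncentral t, 98 df) or 73.0% (normal approximation), so the stated 72% reproduces. For attrition, 50 / 0.95 = 52.6, rounded up to 53, and 5 × 53 = 265.

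**2. What 0.97 says about the two-level factor.** The variance inflation factor is 1 / (1 − r²). If the omitted term were the UUIE count, r = 0.97 would give 1 / (1 − 0.941) = 16.9. Cutting the count at 9 weakens the correlation. As a rough guide, a normal variable correlates √(2/π) = 0.798 with its own median split, and 0.97 × 0.798 = 0.77. The documents give no baseline distribution, so gamma baselines with means of 4.5 to 9 episodes per day were assumed, with UIE and UUIE correlated at about 0.97. The > 9 indicator then correlates about 0.63 to 0.79 with baseline UIE. Inflation is 1 / (1 − 0.397) = 1.7 to 1 / (1 − 0.624) = 2.7. This is no estimation problem. It also falls on the baseline coefficients, not on the treatment contrasts, because treatment is randomised within the stratum.

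**3. Cost of including or omitting the stratum.** Simulated trials had five arms of 50, blocks of five within stratum × sex, 12% men, baseline slope 0.4 and residual SD 3.5 (6,000 runs per cell). Baseline UIE was gamma with mean 5.5 and SD 3.5, which puts 15% above 9. The step is an assumed extra shift in the > 9 stratum beyond the straight line in baseline UIE.

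| Step (episodes/day) | SE without | SE with | Change on adding | Power without / with | Type I without / with |
|---|---|---|---|---|---|
| 0 | 0.7000 | 0.7008 | +0.1% | 72.4% / 72.2% | 0.050 / 0.050 |
| 1 | 0.7008 | 0.7000 | −0.1% | 73.4% / 73.4% | 0.048 / 0.049 |
| 2 | 0.7058 | 0.7001 | −0.8% | 71.3% / 72.0% | 0.048 / 0.049 |
| 3 | 0.7146 | 0.7009 | −1.9% | 71.0% / 72.3% | 0.046 / 0.048 |

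The two models in a row are fitted to the same data. Differences between rows include simulation error of about √(0.72 × 0.28 / 6000) = 0.6 points of power.

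**4. A higher baseline.** With mean 9 and SD 4.5 (43% above 9) and other settings unchanged (3,000 runs), adding the factor changed the SE as follows:
- no step: 0.6991 to 0.7000 (+0.1%);
- step of 2: 0.7118 to 0.7013 (−1.5%), power 72.0% to 72.9%;
- step of 3: 0.7255 to 0.7010 (−3.4%), power 69.9% to 71.9%.

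Type I error without the factor was 0.047 to 0.054, against a simulation error of √(0.05 × 0.95 / 3000) = 0.004.

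**5. Degrees of freedom.** The reduced model has 1 intercept, 4 treatment terms, 1 baseline term and 1 sex term. That leaves 265 − 7 = 258 with all participants included, and 257 with the stratum added.

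**The case against.** The best defence is that the SAP is arguing redundancy, not numerical instability. Continuous baseline UIE is already in the model, sex is kept, and a cut of a closely related count adds little. The stratum is also the cruder measure: SAP 15.3 says it was formed without the valid-diary-day rule that governs the analysed baseline. The change is prespecified and listed in 16.0, and the protocol leaves analysis detail to the SAPs. The planned power came from an unadjusted t-test and never relied on this factor. The gain from restoring it needs a step at 9 per day that nothing in the documents establishes; if only 6% of participants were above 9, that stratum would hold about 0.06 × 265 = 16 people, roughly 3 per arm.

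Most of this stands, and it keeps the point minor. It does not rescue the stated reasons. The factor is redundant only if the upper stratum follows the fitted straight line, and 0.97 between counts does not show that. Nor does redundancy with baseline UIE match the reason in 16.0.

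A reader might infer more than the documents support:
- **That the primary test is invalid.** Type I error stays near 5% without the stratum.
- **That the departure is concealed.** Section 16.0 declares it.
- **That 0.97 is irrelevant.** It carries over in weakened form; it just does not justify dropping the factor.
- **That omission can only lose precision.** It gains about 0.1% when the stratum adds nothing.
- **That no analysis of the primary endpoint uses the protocol model.** None is visible in 10.1, but parts of section 10 are missing from the public copy.

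**Conclusion.** The point holds as a minor one. The SAP's primary model departs from the protocol model and from the allocation, on two differing reasons that do not support the change. The test remains valid, and continuous baseline UIE carries most of the stratum's information. Because stratified blocks already balance the stratum, the main loss is a standard error that is slightly too large when the stratum has an effect of its own.

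The trade is lopsided but small. Omission saves about 0.1% in standard error at best. It could cost about 1% to 3%, or roughly 1 to 2 points of power, if the > 9 stratum departs from the linear relation by 2 to 3 episodes per day. That range rests on assumed gamma baselines, an assumed step and a residual SD of 3.5. With a smaller residual SD the same step would weigh more in relative terms. The conclusion that the 0.97 figure does not justify the omission does not depend on the size of the step.

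**What to change.** In Stage 2 SAP 10.1, fit the primary ANCOVA and its observed-data version with baseline UIE as covariate and with treatment, sex and the UUIE stratum as factors, as in protocol Table 10-3. Use the stratum entered at randomisation, in line with the SAP 10.0 rule on mis-stratified participants. The model without the stratum can stay as an optional sensitivity analysis. Remove or correct the correlation rationale in 10.1, and bring 16.0 into line with it. While editing, check whether the ≤ 9 / > 9 factor in the 10.2 volume-voided model is meant to be UUIEs.

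The cost is one model term, one degree of freedom (258 to 257), up to about 0.1% in standard error if the stratum adds nothing, and a few lines of SAP text. No new data are needed, since the stratum is already recorded in the randomisation system.

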10.2 SECONDARY EFFICACY VARIABLES

The secondary efficacy variables are:

- change from baseline to week 12 in the average number of micturition episodes per day (toilet voids or catheterizations)
- change from baseline to week 12 in the average volume voided per micturition

The number of micturition episodes per day will be calculated based on a consecutive 3-day average. This will be derived in a manner analogous to the average number of UIEs per day.

The average volume voided per micturition will be calculated using the bladder diary records within the 24-hour period where participants were required to collect and record the urine volume from each urinary episode. To obtain this value, the total volume voided (from toilet voids or catheterizations) will be calculated as the sum of the volume voided from the bladder diary records where urine volume was collected within this 24-hour period. The total volume voided will then be divided by the number of micturitions in the same 24-hour period that were included in the sum.

Only data from “valid diary days” will be used in the calculations of the averages discussed above.

[figure not shown]
The change from baseline in the average number of micturition episodes per day will be analyzed using an ANCOVA model with baseline as covariate and treatment group and sex (male, female) as factors.

The change from baseline in the average volume voided per micturition will be analyzed using an ANCOVA model with baseline as covariate and treatment group, sex (male, female) and baseline UIEs (≤ 9 or > 9 episodes/day) as factors.

CONFIDENTIAL

BOTOX® (Botulinum Toxin Type A)
Purified Neurotoxin Complex

[figure not shown]
Page 17

CONFIDENTIAL

BOTOX® (Botulinum Toxin Type A)
Purified Neurotoxin Complex

[figure not shown]
Page 18

CONFIDENTIAL

BOTOX® (Botulinum Toxin Type A)
Purified Neurotoxin Complex

Page 19

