15.3 DERIVED VARIABLES

The following criterion will be used to determine the category of urinary episode for each entry in a participant's bladder diary.

1. A participant has a **micturition episode** if the participant response is yes to either one of the following question in the bladder diary:
 - Did you urinate into the toilet or collection container?
 - Did you use a catheter to urinate?
2. A participant has a **urinary incontinence episode (UIE)** if the participant response is yes to the following question in the bladder diary:
 - Did you have accidental urinary leakage?
3. A participant has a **urinary urgency incontinence episode (UIIE)** if the participant response is yes to both of the following two questions for one episode in the bladder diary:
 - Did you have accidental urinary leakage?
 - Was this episode associated with a sudden and urgent need to urinate?
4. A participant has a **urinary urgency episode (UUE)** if the participant response is yes to the following question in the bladder diary:
 - Was this episode associated with a sudden and urgent need to urinate?
5. A participant has a **nocturia episode** if the participant response is yes to the following question in the bladder diary:
 - Did this episode wake you from night sleep?

[figure not shown]
6. A participant has a **catheterization episode** if the participant response is yes to the following question in the bladder diary:

- Did you use a catheter to urinate?

The number of UIEs per day will be recorded in the participant bladder diary over 3 consecutive days at any time during the screening period for the screening diary, and over 3 consecutive days during the week prior to each post baseline visit. The average number of UIEs per day will be calculated as the total number of episodes recorded in the 3-day bladder diary divided by the total number of valid diary days (see [Section 15.2](#)). The average number of micturition episodes, UUIEs, UUEs, and nocturia episodes will be derived in a similar manner.

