To determine stratification groups (≤ 9 or > 9 UUIEs/day) for participants during randomization, the concept of valid diary days was not used by investigators to calculate the average number of UUIEs per day. Instead, all UUIEs recorded on the bladder diary from the beginning to the end of the first 3 consecutive 24 hour periods during the screening period was used irrespective of whether it was a valid dairy day or not. After database lock, this calculation will be repeated see if the values obtained by Allergan (i.e. actual stratification group) is the same as that recorded by investigators in the IVRS (planned stratification group). Note that this is done only to check for mis-stratifications. All other analyses or derivations using bladder diary data will be based on valid diary days.

The average volume voided per micturition will be calculated using the bladder diary records within the 24-hour period where participants were required to collect and record the urine volume from each urinary episode. To obtain this value, the total volume voided will be calculated as the sum of the volume voided from the bladder diary records where urine volume was collected within this 24-hour period. The total volume voided will then be divided by the number of bladder diary records that were included in the sum.

CONFIDENTIAL

BOTOX® (Botulinum Toxin Type A)
Purified Neurotoxin Complex

Page 34

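### Stage 2 secondary models: the voided-volume model names a UIE split where randomisation used UUIEs, and the micturition model leaves that stratum out

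*SAP*

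**What the plan says.** Protocol section 7.3 stratifies Stage 2 randomisation by sex and by baseline UUIEs, at most 9 or more than 9 per day. The endpoint table in protocol section 10.3.2.2 assigns both secondary endpoints to the change-from-baseline ANCOVA. Protocol Table 10-3 says that this model adjusts for treatment, the stratification variables and the baseline value.

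Stage 2 SAP section 10.2 departs from this in two places:

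- **Voided volume per micturition.** The terms are "baseline as covariate and treatment group, sex (male, female) and baseline UIEs", with the cut at 9 per day.
- **Micturition frequency.** The change in "micturition episodes per day will be analyzed using an ANCOVA model with baseline as covariate and treatment group and sex (male, female) as factors". No incontinence stratum appears.

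Other parts of the Stage 2 SAP bear on these models:

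- Section 15.3 describes how the stratum was formed: "To determine stratification groups (≤ 9 or > 9 UUIEs/day) for participants during randomization", all recorded UUIEs were counted, whether or not the diary day was valid. It then says: "All other analyses or derivations using bladder diary data will be based on valid diary days".
- Section 10.0 sets the rule for errors at randomisation: "Mis-stratified participants, if any, will be analyzed based on the stratification group to which the participants were assigned to". It also says that "missing values will be imputed (see details below) only for the primary efficacy variable".
- Section 16.0 acknowledges the protocol position "that all ANCOVA models will include both stratification factors (sex and baseline UUIEs per day) as independent variables". It then says that some models keep sex only, because baseline UUIEs correlate highly with some diary-based dependent variables. It does not say which models.

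**The concern.** In the voided-volume model, the printed factor is not the one used at randomisation. Section 15.3 defines a UIE as any leakage, and a UUIE as leakage with a sudden, urgent need to urinate. The two abbreviations therefore describe different variables, and a programmer following the text would build the wrong one.

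In the micturition model, a randomisation factor is dropped for a reason that, as worded, does not support dropping it. A factor that predicts the outcome is normally one to adjust for. If the stratum is prognostic beyond baseline micturition frequency, leaving it out widens the confidence intervals and makes the tests slightly conservative.

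What is at stake is clear programming and some precision on two secondary endpoints.

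**Working it through.** **1. The plan's own figure.** Inputs from SAP section 13.0: difference 1.8, SD 3.5, 50 per arm, two-sided 5%. Noncentrality = 1.8 / (3.5 × √(2/50)) = 1.8 / 0.70 = 2.57 on 98 df, giving power 0.721 against the stated 72%. Attrition: 50 / 0.95 = 52.6, rounded up to 53; 53 × 5 = 265. Both reproduce. They concern the primary endpoint and are unaffected here.

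**2. Is the UIE wording a slip?**

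- Every other factor cut at 9 per day in the readable Stage 2 SAP (sections 10.1, 15.3 and 16.0) is UUIEs.
- The cut in the voided-volume model is identical.
- The planned-stratum rule in section 10.0 needs a group recorded at randomisation; none exists for UIEs.
- Section 15.3 mistypes the same abbreviation: "urinary urgency incontinence episode (UIIE".

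All of this points to a slip.

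**3. What the literal reading would do.** The factor would come from valid diary days and any leakage, whereas the stratum came from all recorded UUIEs. Every UUIE is also a UIE, so apart from the diary-day rule participants could only move upward across the cut. Assume baseline UIE mean 4 to 7 and SD 3 to 4.5, with 85% to 95% of UIEs being UUIEs, and correlation 0.97 (quoted in section 10.1). Then about 2 to 27 of 265 participants would change category.

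**4. Standard-error cost of the UIE split.** Let R² be the share of residual variance that the true stratum explains (assumed; the documents give no value), and φ the correlation between the two yes/no splits. Relative to using the true stratum, the cost is √((1 − φ²R²)/(1 − R²)) − 1. If the underlying counts behave as normal variables correlated 0.97, with an assumed 20% above the cut, φ is about 0.83. At R² = 10%: √((1 − 0.689 × 0.10)/0.90) − 1 = √1.0346 − 1 = 1.7%. A simulation with 250 observed participants and stratified blocks of 5 also captures the fact that a UIE split is not balanced by design; it gives the third column below.

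**5. Cost of omitting the stratum from the micturition model.** Secondary variables are not imputed, so about 250 participants contribute (50 × 5 by design; 265 less 5% is 252). Parameters: intercept 1 + baseline 1 + treatment 4 + sex 1 = 7. Residual df = 250 − 7 = 243, or 242 with the stratum added. Standard-error inflation from omission is 1/√(1 − R²) − 1. With the stratum fully balanced across arms, actual type I error is 2 × P(T₂₄₃ > 1.9698/√(1 − R²)).

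| Assumed R² | Omission: SE inflation | UIE split: SE cost (simulated) | Omission: type I error |
|---|---|---|---|
| 0% | 0% | 0.1% | 5.0% |
| 1% | 0.5% | 0.2% | 4.9% |
| 5% | 2.6% | 0.9% | 4.4% |
| 10% | 5.4% | 2.0% | 3.9% |

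Simulation with baseline correlated 0 to 0.9 with UUIEs gives type I error of 4.1% to 4.4% under omission at R² = 10%, against about 5.1% with the stratum included.

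**6. Cost of including a useless stratum.** At R² = 0, including it raises the standard error by 0.02%, 0.04% and 0.09% when baseline correlates 0, 0.5 and 0.9 with UUIEs. Collinearity with the baseline covariate therefore does little harm to the treatment comparison, because the stratum is balanced across arms.

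**The case against.** The strongest reply is that the micturition omission is a declared choice. Section 16.0 states the protocol rule, says that some models depart from it, and gives a reason covering several diary variables. Micturition frequency is one of those. A reader might infer an undisclosed departure from the protocol; the documents do not support that. Nor can one say that no supporting correlation exists. The only coefficient in the readable text, 0.97, concerns UIEs with UUIEs, but pages next to section 10.2 are missing from the public copy and may hold more. This stands, and it limits the point to the wording of the reason and an inexpensive improvement.

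A second reply is that the same argument would put the stratum back into the primary model. Inclusion would be cheap there too. But section 10.1 names that model and gives a specific reason, a 0.97 correlation between UIEs and UUIEs. The primary model is not part of this point.

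A third reply is that if the UIE wording is a slip, the literal-reading problems do not arise. That is fair. They show why the text should be corrected, and they are not evidence that the sponsor means to substitute UIEs. For the same reason, the silence of section 16.0 on a UIE factor is not a failure to disclose.

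Finally, every non-zero gain rests on an assumed R², and the balance argument assumes effective blocking within strata. Protocol section 7.3 gives no block scheme. Both limits stand.

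**Conclusion.** The point holds and is minor. The voided-volume model is wrong as written: it names a factor that was not randomised, very probably by a typing error. Used literally, the UIE split would cost roughly 0.1% to 2% in standard error for an assumed R² of 0% to 10%, taking the 0.97 correlation to apply to baseline counts.

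The micturition model would be improved by adding the stratum. Assuming effective stratified blocking, the gain is 0% to about 5% in standard error over the same range; the true value is unknown and may be near zero.

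A reader might infer bias or excess false positives. Neither follows: omitting a balanced stratum makes the test conservative if anything. Only secondary endpoints are affected, and the stated power and sample size do not change.

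**What to change.** 1. **Section 10.2, voided volume (correction).** Replace the UIE factor with the baseline UUIE stratum, at most 9 or more than 9 episodes per day, as recorded at randomisation. The planned-stratum rule in section 10.0 then applies to it directly.
2. **Section 10.2, micturition (improvement).** Add the same recorded UUIE stratum as a factor.
3. **Section 16.0, if the sponsor keeps the omission.** Name the micturition model and give the sponsor's own reason for leaving the stratum out.

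The cost is SAP wording, plus one residual degree of freedom in the micturition model (243 to 242) and under 0.1% in standard error if the stratum explains nothing. No new data are needed; the stratum is already held in the randomisation system.
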